#### **10.5 STUDY LENS SUPPLY**

The investigational Model ZFR00 or ZYR00 lenses and the Model ZLB00 control lenses will be obtained from site consignments, supplied by JJV following IRB approval. Two lenses should be available for each case, a primary lens and a back-up lens. Unused back-up lenses are to be returned to the site consignment. At the completion of study enrollment, any remaining consignment lenses will be shipped back to JJV following reconciliation of investigational lens inventory by an JJV CRA. Any remaining control lenses will also be returned to JJV. At all times, the storage, access and use of all investigational lenses must be controlled and complete lens accountability maintained (See Section 15.2.1 Lens Accountability).

#### **10.6 OPERATIVE PROCEDURES**

The investigator should use his or her standard, small-incision, cataract extraction surgical technique. Lenses should be folded for implantation and inserted into the capsular bag using one of the JJV-validated insertion systems described in Section 7.2.

Investigators should manage surgical outcomes to ensure that the total postoperative refractive astigmatism is as minimal as possible. The total postoperative astigmatism, including surgically-induced astigmatism, should be targeted to be no greater than 1.0 D. Astigmatism may be managed by incision type and placement only. **No additional refractive procedures are to be performed during the operative procedure or throughout the postoperative study period (e.g., LRI, OCCI, CRI, AK, PRK, LASIK or LASEK).**

Operative case report forms will include the following information:

#### INCISION TYPE AND SIZE

Lenses should be inserted through an incision ranging in size from approximately 2.2-3.0 mm, per the investigator's standard technique when using the UNFOLDER Platinum 1 Series Implantation System or the ONE SERIES Ultra Implantation System. The incision may be clear corneal, limbal or scleral tunnel at the discretion of the investigator.

#### CAPSULORHEXIS SIZE AND METHOD

The anterior capsulotomy should be a continuous, curvilinear capsulorhexis approximately 5.0 to 5.5 mm in diameter to allow slight overlap of the lens optic edge. The anterior capsulotomy method may be manual (rhexis) or laser-assisted.

#### LENS REMOVAL

Lens removal may occur using laser fragmentation combined with phacoemulsification/aspiration or using only phacoemulsification/aspiration.

#### VISCOELASTIC

Viscoelastic materials should be used as is customary for each investigator and recorded on the case report form (CRF).

#### IMPLANT INSTRUMENTATION USED

Lenses should be folded for implantation and inserted into the capsular bag using either the UNFOLDER Platinum 1 Series Implantation System (DK7796 handpiece with the Platinum 1 Series cartridge, Model 1MTEC30) or the ONE SERIES Ultra Implantation System (DK7786 [plunger] or the DK7791 [twist] handpieces with the ONE SERIES Ultra cartridge, Model 1VIPR30).

#### SURGICAL COMPLICATIONS

Should a surgical complication occur, implantation of a study lens will be at the investigator's discretion. In the event of capsular bag or zonular rupture, the lens should not be implanted if the complication may result in lens instability. Additionally, the lens is

not to be implanted in the sulcus. In this case, the investigator may implant his/her choice of a back-up, non-investigational IOL. The subject should be exited from the study if a non-study lens is implanted as a result of a surgical complication during the first-eye implantation; however, the eye will be followed until resolution of the complication prior to exiting the subject. Should a surgical complication occur during the second-eye surgery and result in implantation of a non-study lens, the subject will not be exited from the study; the first eye will continue to be followed per-protocol, although data may be analyzed separately, and the second eye will be followed for safety until resolution of the complication.

### MEDICATIONS

Preoperative, operative and intraoperative medications should be used as is customary for each investigator and will be recorded on the CRF.

### TYPE OF CLOSURE

Wound closure is left to the surgeon's discretion and will be recorded on the CRF.

### ADDITIONAL OPERATIVE INFORMATION COLLECTED INCLUDES:

- Date of surgery
- Operative eye
- Lens power and serial number
- Lens placement
- Other surgical procedures
- Surgical technique according to protocol
- Product complaints
- Serious and/or device-related adverse events

## **10.7 POSTOPERATIVE PROCEDURES**

Postoperatively, subjects will be examined according to the schedule in Section 10.2, Visit Schedule. Only the most recently operated eye will be evaluated at the 1-day and 1-week visits. Both eyes will be evaluated at the 1-month and 6-month visits.

Study technicians responsible for conducting all vision testing will be masked. Therefore, it is recommended that only the investigator/sub-investigator or other designated and trained clinician perform the biomicroscopic slit-lamp exams. To maintain consistency and masking throughout the study, it is recommended that a single individual (study technician or coordinator designated by the investigator) conduct all postoperative study-related vision testing, although a back-up person should also be designated and trained.

Note: Subjects are not to wear contact lenses postoperatively until after completion of this study. Wearing contact lenses may potentially cause corneal edema or topography changes that may influence the visual acuity results. During the study, if correction is required, spectacles should be prescribed.

A postoperative CRF will collect the following information, although not all data are required at every visit (see **Appendix A**):

#### MANIFEST REFRACTION AND REFRACTION ADJUSTMENTS (MASKED PROCEDURE)

Postoperative study manifest refractions are to be performed using the M&S System at a distance of 4.0 meters. Manifest refraction (MR) is to be performed using the Maximum Plus refraction method as detailed in **Appendix C**.

Because 4.0 meters is not optical infinity, refraction adjustments are necessary to ensure proper vision testing taking into account test distance and refraction distance.

**Appendix D** lists the refraction adjustments required for the various vision tests using the BCDVA refraction.

#### DISTANCE VISUAL ACUITY TESTING (MASKED PROCEDURE)

Distance visual acuity will be measured postoperatively under photopic lighting conditions (85 cd/m^2, 80–110 cd/m^2 acceptable) using the M&S System at a test distance of 4.0 meters. For eyes unable to achieve a postoperative BCDVA of Snellen 20/40 (i.e., LogMAR 0.3, number of letters correct 70), a reason must be specified. Instructions for using the M&S System are detailed in **Appendix E**, and for distance visual acuity in **Appendix F**.

#### LOW CONTRAST DISTANCE VISUAL ACUITY (10%) (MASKED PROCEDURE)

Low contrast (10% contrast) distance visual acuity will be measured under photopic conditions (85 cd/m^2, 80-110 cd/m^2 acceptable) using the M&S System at a test distance of 4.0 m. Instructions for low contrast distance testing are detailed in **Appendix F**.

The following distance visual acuity measurements are to be performed per the visit schedule in **Appendix A**:

Test	Test Distance	Illumination	Type of Testing	Refraction Adjustment
UCDVA	4 m	Photopic (85 cd/m  )	Monocular Binocular	+0.25 D adjustment only
BCDVA	4 m	Photopic (85 cd/m  )	Monocular Binocular	No adjustment; ETDRS Rx only
BCDVA Low Contrast	4 m	Photopic (85 cd/m  )	Monocular Binocular	No adjustment; ETDRS Rx only

#### INTERMEDIATE VISUAL ACUITY (MASKED PROCEDURE)

Intermediate visual acuity will be measured under photopic conditions (85 cd/m^2, 80-110 cd/m^2 acceptable) using the M&S System at a test distance of 66 cm. Instructions for using the M&S System are detailed in **Appendix E** and for intermediate testing in **Appendix G**.

The following intermediate visual acuity measurements are to be performed per the visit schedule in **Appendix A**:

Test	Test Distance	Illumination	Type of Testing	Refraction Adjustment
UCIVA	66 cm	Photopic (85 cd/m  )	Monocular Binocular	No adjustment
DCIVA	66 cm	Photopic (85 cd/m  )	Monocular Binocular	-0.25 D added to ETDRS sphere Rx

#### NEAR VISUAL ACUITY (MASKED PROCEDURE)

Near visual acuity will be measured under photopic conditions (85 cd/m^2, 80-110 cd/m^2 acceptable) using the Good-Lite self-calibrating, retro-illuminated box with 100% contrast ETDRS near charts at a test distance of 40 cm.

Instructions for using the ETDRS near chart, including setting appropriate lighting conditions, and the visual acuity conversion chart between the number of ETDRS letters read and Snellen equivalents are provided in **Appendix H**.

The following near visual acuity measurements are to be performed per the visit schedule in **Appendix A**:

Test	Test Distance	Illumination	Type of Testing	Refraction Adjustment
UCNVA	40 cm	Photopic (85 cd/m  )	Monocular Binocular	No adjustment
DCNVA	40 cm	Photopic (85 cd/m  )	Monocular Binocular	-0.25 D added to ETDRS sphere Rx

#### DEPTH OF FOCUS TESTING (MASKED PROCEDURE)

Monocular, best corrected distance depth of focus testing will be performed at the 1-month visit on the first eye only for all subjects, and binocular best corrected distance depth of focus testing will be performed at the 6-month visit on all subjects.

Depth of focus testing will be performed under photopic conditions (85 cd/m^2, 80-110 cd/m^2 acceptable) using the M&S System at 4.0 meters with the ETDRS refraction in place (no adjustment necessary for test distance). The subject is to be defocused in -0.50 D increments with spherical minus lenses; at each defocus increment, a LogMAR measurement is obtained. Testing is to be conducted from +2.00 D through -4.00 D of defocus. Further instructions for defocus testing are detailed in **Appendix I**.

The following defocus curve measurements are to be performed per the visit schedule in **Appendix A**:

Test	Test Distance	Illumination	Type of Testing	Refraction Adjustment
Monocular Depth of Focus	4 m	Photopic (85 cd/m  )	Monocular	No adjustment; ETDRS Rx only
Binocular Depth of Focus	4 m	Photopic (85 cd/m  )	Binocular	No adjustment; ETDRS Rx only

#### PUPIL SIZE

Photopic (without glare), and mesopic with and without glare pupil sizes will be measured postoperatively during the study. For consistency, the same method of measurement should be used throughout the study.

Photopic pupil size measurements are to be performed under the same lighting conditions at which photopic distance visual acuity is tested. Pupil sizes under the other lighting conditions will be measured during the contrast sensitivity testing procedures. Instructions for measuring pupil size are detailed in **Appendix J**.

DISTANCE CONTRAST SENSITIVITY TESTING (MASKED PROCEDURE)

Best corrected distance contrast sensitivity will be tested under mesopic with and without glare and photopic without glare conditions using the M&S System for sine-wave gratings at 1.5, 3.0, 6.0, 12.0 cycles per degree (cpd) (mesopic and mesopic with glare) and 3.0, 6.0, 12.0 and 18.0 cpd (photopic without glare). **The test distance is 8 feet (2.5 meters).** Best corrected distance contrast sensitivity is to be performed with a +0.12 D refractive adjustment to the sphere of the manifest refraction. Detailed instructions for contrast sensitivity testing are provided in **Appendix K**.

The following contrast sensitivity measurements are to be performed per the visit schedule in **Appendix A**:

Contrast Sensitivity Test	Test Distance	Spatial Frequency	Type of Testing	Refraction Adjustment
Photopic (85 cd/m  ) without glare	2.5 m	3, 6, 12 and 18 cpd	Monocular Binocular	+0.12 D added to ETDRS sphere Rx
Mesopic (3 cd/m  ) without glare	2.5 m	1.5, 3, 6 and 12 cpd	Monocular Binocular	+0.12 D added to ETDRS sphere Rx
Mesopic (3 cd/m  ) with glare	2.5 m	1.5, 3, 6 and 12 cpd	Monocular Binocular	+0.12 D added to ETDRS sphere Rx

BIOMICROSCOPIC SLIT-LAMP EXAM

A biomicroscopic slit-lamp exam must be performed at each postoperative visit to determine the presence or absence of any medical or lens findings, complications or adverse events. IOL decentration and tilt are to be determined subjectively. The center of the lens relative to the pupil can be used to determine IOL decentration, with the diffractive rings used as a guide to locate the center of the IOL. Note that the pupil center may not always be aligned with the visual axis of the eye; therefore, the investigator should consider deviations in pupil center from visual axis when reporting IOL decentration.

Findings of aqueous cells and flare, corneal edema, posterior capsule striae (wrinkles), posterior capsular opacification and IOL glistenings are to be rated using standardized grading scales of 0 to +4 (0 = none, +4 = severe) during the slit-lamp biomicroscopy. The specific grading scales are provided in **Appendix L**.

ND:YAG CAPSULOTOMY

If an Nd:YAG capsulotomy is necessary, it is recommended that the procedure be performed at least 1 week prior to a study exam; this is particularly important for the

6-month study visit, as this is the key study exam for evaluation of safety and effectiveness.

#### DILATED FUNDUS EXAM

A dilated fundus exam is to be performed at the 6-month visit to evaluate retinal status and fundus visualization.

#### INTRAOCULAR PRESSURE

Intraocular pressure (IOP) is to be measured using the investigator's usual method. It is recommended that the same method be used for all study subjects at the site for the duration of the study.

#### OCULAR SYMPTOMS (NON-DIRECTED; SPONTANEOUS)

Subjective ocular symptoms are to be assessed at each postoperative visit by asking "Are you having any difficulties with your eyes/vision?" Subjects should not be prompted for specific responses; however, if a subject reports halos, night glare or starbursts, the level of severity should be determined (mild, moderate or severe).

#### MEDICATIONS

Postoperative ocular medications should be used as is customary for each investigator and recorded in the source document for each subject. Medications will be recorded on a medication log CRF as applicable.

#### ADVERSE EVENTS

Subjects should be assessed at each visit for occurrence of and/or change in status of any adverse events, particularly serious and/or device-related adverse events. See Section 11.0, Adverse Events, for further information.

#### QUESTIONNAIRES

Questionnaires will be administered at the 1-month and 6-month visits to collect information regarding spectacle usage, visual symptoms, visual quality and subject satisfaction. In order to minimize any effect the doctor-patient relationship may have on a subject's responses on the questionnaire, the study questionnaires will be self-administered by the subjects. The questionnaires are to be administered at the start of the 1-month and 6-month study visits, prior to any visual acuity testing.

In addition, if a subject is seen after the 1-month postoperative visit for an unscheduled visit due to an optical/visual symptom complaint, the PRO Visual Symptoms Questionnaire (PRVSQ) will be administered at that visit, as well as prior to any secondary surgical intervention for an optical/visual symptom complaint. If additional unscheduled visits and/or a secondary surgical intervention due to the same

optical/visual symptom complaint occur within 2 weeks of each other, it is not necessary to complete the PRO Visual Symptoms Questionnaire a second time.

The optical visual symptom complaints that trigger the PRO Visual Symptoms Questionnaire include any of the seven symptoms from the PRVSQ: halos, glare, starbursts, sensitivity to light, streaks of light, occlusions, or poor light vision.

If the subject indicates in the PRO Visual Symptoms Questionnaire that s/he has visual symptoms or other problems with their vision that are bothersome enough to want the lenses removed and replaced, the investigator will document a determination for whether or not, in their opinion, the problem is related to the optical properties of the lens.

## **10.8 EXIT OF SUBJECTS**

An Exit CRF will be completed for all subjects, either when they complete the study or if they exit early.

It is the responsibility of the investigator to provide complete follow-up data to JJV for each subject, and every attempt should be made to gather that complete follow-up data for all subjects enrolled, as missing data can have a negative effect on the study results. Patients who would be traveling, relocating or otherwise unavailable for postoperative follow-up visits should not be enrolled in this clinical study.

A subject will be considered a "screen failure" if he/she does not meet the eligibility criteria or if consent is withdrawn prior to randomization.

A subject will be considered "discontinued prior to treatment" if the subject is randomized but does not undergo surgery or receive a study lens for various reasons including: the planned implant being aborted due to surgical complications, the subject withdrawing consent prior to treatment or the subject died prior to treatment.

Subjects will be "discontinued" from the study if one study lens (if implanted unilaterally) or both study lenses (if implanted bilaterally) are removed or if the subject dies.

If a subject receives at least one study lens, he/she is to be followed according to the schedule in Table 2 (Section 10.2) for visit windows.

Subjects will be considered "lost-to-follow-up" from the study only if irretrievably lost for unavoidable reasons such as: subject moved/unable to locate, subject ill/unable to travel, subject uncooperative/refuses further study participation. In the event of subject relocation, effort must be made by the investigator to secure follow-up information (i.e., slit-lamp findings and general visual acuity, etc.) from the subject's new physician.

If a subject is exited early from the study, the investigator must indicate the reason for study exit on the CRF. In the event of a lens removal or other serious adverse event, the subject may be exited from the study; however, effort must be made by the investigator to follow the subject until resolution of the adverse event before exiting the subject from the study.

Following study completion or early exit, subjects will be informed about which lens model they received. Additionally, all study subjects are to be instructed to undergo regular eye examinations at least yearly and also to return to their doctor if any eye complications are experienced.

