## **10. EXPERIMENTAL PLAN**

### **10.1 OVERVIEW**

This study will be conducted in accordance with U.S. Code of Federal Regulations, the Declaration of Helsinki, ISO 14155:2011 and all other applicable laws and regulations. The study will not begin until regulatory and IRB approvals have been obtained.

This study will be a prospective, multicenter, bilateral, randomized, comparative subject/evaluator-masked clinical investigation conducted at up to 14 sites. Up to 260 subjects will be enrolled to achieve approximately 220 randomized and bilaterally implanted subjects, resulting in approximately 195 evaluable subjects (65 in each test group and 65 in the control group) at 1 and 6 months. After informed consent is obtained and confirmation that all eligibility criteria are met, the eye(s) may be treated.

After signing the informed consent form, subjects meeting all eligibility criteria will be randomized to receive lenses from the same lens group in both eyes, either the investigational Model ZFR00 or Model ZYR00 IOLs, or the Model ZLB00 control IOL. For each subject, the investigator will choose which eye to operate on first at his/her discretion based on his/her standard clinical practice (e.g., the eye with the worse cataract, poorer best corrected distance vision and/or more severe optical/visual complaints). All subjects are intended to have bilateral cataract surgery with the second-eye surgery occurring after the 1-week postoperative exam for the first eye, but no more than 30 days after the first-eye surgery. All subjects will be examined through 6 months postoperatively according to the visit schedule described in Section 10.2, Visit Schedule.

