### **11.5 ADVERSE EVENT FOLLOW-UP**

For every adverse event, appropriate measures should be undertaken to treat and/or monitor the subject until resolution occurs. The subject's files are to include all pertinent medical data relating to the event including the subject's medical records, medical reports and/or judgments from colleagues or outside specialists who assisted in the treatment and follow-up of the subject. The investigator should keep JJV closely informed as to the outcome of serious and/or device-related adverse events, thereby allowing JJV to comply with the appropriate regulatory reporting requirements. An SAE/ADE CRF should be completed each time the subject returns to the investigator or other specialist(s) for follow-up of a serious and/or device-related adverse event until resolution of the event. Any subject who is to be exited from the study due to a serious and/or device-related adverse event should be followed until the outcome is determined prior to being exited from the study.

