### **20.1 ANALYSIS POPULATION**

The safety population (SP) of all subjects implanted who have available data will be used for all analysis. No data imputation will be performed for missing data. For the monocular endpoints, the safety population will consist of first eyes implanted with a study IOL; for binocular endpoints, the safety population will consist of subjects implanted with the same IOL in both eyes. The primary analysis population will be the

safety population (SP) for all endpoints. Second eye data will only be reported for monocular safety endpoints as supportive data.

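### Protocol Sections 10.8, 11.5 and 19 do not settle whether a subject with a serious adverse event and the study lens in place stays on the visit schedule, so later safety data can be lost in relation to outcome

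*Protocol*

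**What the plan says.** **Follow-up rule.** Protocol Section 10.8 states: "If a subject receives at least one study lens, he/she is to be followed according to the schedule in Table 2". Section 10.1 gives the end point of that schedule: "All subjects will be examined through 6 months postoperatively according to the visit schedule described in Section 10.2, Visit Schedule". Section 10.8 also has a discontinued category, entered on removal of the study lens or lenses or on death, and a lost-to-follow-up category for irretrievable loss.

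**Exit rule.** The same section then says: "In the event of a lens removal or other serious adverse event, the subject may be exited from the study". A condition is attached: "effort must be made by the investigator to follow the subject until resolution of the adverse event before exiting the subject from the study". Section 11.5 asks for follow-up until the outcome is known, and introduces it with "Any subject who is to be exited from the study due to a serious and/or device-related adverse event". Section 19 adds that the investigator or the sponsor may stop a subject's participation at any time.

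**Analysis.** Protocol Section 20.1: "No data imputation will be performed for missing data". SAP Section 2.1 likewise uses available data, and it keeps whatever was collected before an exit. The proportion of first eyes at 20/40 or better BCDVA is tested against the ISO SPE rate at 1 month (Protocol 20.3), and at 1 and 6 months in SAP 7.2. SAP 7.6 compares ISO-listed complication rates with the SPE rates at 6 months.

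**The concern.** Two sites could treat the same eye differently and both comply. One keeps a subject with, say, a retinal detachment and the lens in place on the schedule to 6 months. The other follows the event until it resolves and then exits the subject. An exit of the second kind fits neither the discontinued nor the lost-to-follow-up category.

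The events listed in Section 11.1, such as cystoid macular edema, retinal detachment and persistent corneal edema, plausibly lower acuity. If the event leads to exit and the eye has no BCDVA at the visit, the eye leaves the 20/40 denominator instead of counting as a failure. The error runs one way: it makes a shortfall against the SPE rate harder to see. Questionnaire answers and any second or later event are lost as well. The implanting investigators are unmasked, so exits could also differ by lens.

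**Working it through.** **1. The plan's own figure on loss.** Section 20.6 assumes 10% dropout: 65 / (1 − 0.10) = 72.2, rounded up to 73 implanted per group. This reproduces. It allows for the number of losses but not for losses related to outcome.

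**2. Which data are exposed.**
- The triggering event: kept (SAP 2.1).
- 1-month BCDVA: lost only if exit precedes that visit, at 30 to 60 days after the second implant.
- 6-month BCDVA, questionnaires and ISO comparison: lost after any earlier exit.
- Raised pressure, corneal edema and iritis: under Section 11.1, Note 2, these are serious only if present at the final visit or sight-threatening when they occur. An eye that has left cannot be classified at the final visit.

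**3. Boundary check on the 20/40 test.** Inputs: n = 65 evaluable or 73 implanted first eyes (Section 20.6) and one-sided alpha 0.05 (SAP 2.3 default). The documents do not give the SPE rate p0, so 90% to 97% is an assumed range. With f failing eyes, p = P(X ≤ n − f), X ~ Bin(n, p0). If one failing eye exits unmeasured, p = P(X ≤ n − f), X ~ Bin(n − 1, p0).

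| Assumed SPE | n = 65: failures to reject | p, then p after one exit | n = 73: failures to reject | p, then p after one exit |
|---|---|---|---|---|
| 90% | 12 | 0.026 → 0.052 | 13 | 0.028 → 0.053 |
| 92.5% | 10 | 0.0225 → 0.0487 | 10 | 0.046 → 0.089 |
| 95% | 7 | 0.043 → 0.100 | 8 | 0.029 → 0.068 |
| 97% | 5 | 0.046 → 0.126 | 6 | 0.023 → 0.065 |

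One exit reverses the decision in seven of the eight cases. The exception is n = 65 with 92.5%.

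**4. Power to detect a true shortfall, n = 65.** Let failures F ~ Bin(65, 1 − π), where π is the true 20/40 rate, and let each failing eye exit unmeasured with probability e, giving K exits. Reject if P(X ≤ 65 − F) < 0.05 with X ~ Bin(65 − K, p0). Both e and π are assumptions.

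| SPE / true rate | e = 0 | e = 5% | e = 25% |
|---|---|---|---|
| 90% / 80% | 67% | 61% | 36% |
| 95% / 88% | 68% | 62% | 37% |
| 97% / 90% | 79% | 75% | 54% |

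The fall is 4 to 6 points at e = 5% and 25 to 31 points at e = 25%. The observed rate becomes about π / [π + (1 − π)(1 − e)]. At e = 25% that is 0.80/0.95 = 0.842, 0.88/0.97 = 0.907 and 0.90/0.975 = 0.923, a rise of 2 to 4 points. At e = 5% the rise is about 0.5 to 0.8 points.

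**5. Later adverse events.** With assumed SPE rates of 0.3% to 3% and n = 73, rejection needs 2 to 6 first eyes with the event. Losing one such event and its eye at that boundary gives p = 0.195 (0.3%), 0.051 (0.5%), 0.162 (1%), 0.057 (2%) and 0.065 (3%). All exceed 0.05. This applies only to an event that arises or is classified after exit.

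**The case against.** The passages can be read together: a general rule to follow Table 2, a mandatory discontinuation category, and a permissive exception that carries a follow-up duty. Section 10.8 also asks for every attempt at complete data. Following to resolution keeps unresolved eyes longest, and those are the eyes most likely to see poorly. Section 11.5 protects follow-up; it does not grant permission to exit. Any exact test near its boundary turns on one eye. The n = 65 figure is already net of dropout, so removing further eyes partly double-counts loss. The 25% exit rate has no source in the documents. BCDVA against the SPE rate is not a primary endpoint, and the study gathers preliminary information for choosing a design.

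Most of this stands, and it limits the size of the point. It does not remove it. A general plea for complete data does not override an express permission to exit, and neither resolution nor a known outcome requires the 1-month or 6-month visit. An event can reach its outcome with permanent loss of vision, and the eye can then leave without a study BCDVA. The protocol's intent elsewhere is to retain subjects: after suspension of the study, treated subjects complete the schedule (Section 19), and after a second-eye complication with a non-study lens the first eye stays on protocol (Section 10.6).

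A reader might infer that serious events themselves vanish from the safety analysis. They do not: SAP 2.1 keeps pre-exit data, and Appendix I of the SAP plans cumulative tables.

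**Conclusion.** The point holds as an unresolved conflict between the follow-up rule and the exit provisions. It permits outcome-related loss of post-exit BCDVA, questionnaires, and new or persistent events. The 6-month comparisons are the most exposed; the 1-month test is affected only by exits before that visit.

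The size is conditional. Exit is optional, so its frequency cannot be derived, and the documents give no SPE rates. The 4 to 31 point fall in power spans illustrative exit rates of 5% to 25% among failing eyes; it is not a forecast. The upper end would require a quarter of failing eyes to have a qualifying event with the lens in place and to be exited before the visit.

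Two further readings go beyond the text. One is that the primary DCIVA result is at risk; nothing here shows that. The other is that the investigator alone decides on exit: Section 10.8 names no decision-maker, and Section 19 names the investigator or the sponsor. No sample-size figure changes. This is a cheap improvement, not a flaw that invalidates the design.

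**What to change.** 1. Reconcile Protocol Sections 10.8, 11.5 and 19 on data collection. State that an adverse event alone does not end it while a study lens is in place, and that the 1-month and 6-month assessments continue unless the subject withdraws consent or cannot attend. Changing Section 10.8 alone would leave the general discretion in Section 19 untouched.
2. Keep the Section 11.5 duty to follow to outcome for any subject who still leaves. Deleting that sentence would remove a safeguard.
3. Add to SAP Section 7.2 a sensitivity run of the 20/40-versus-SPE test. Count as not achieving 20/40 any first eye that was exited after an ocular serious or device-related event in that eye and has no BCDVA at the visit. The limit to ocular events in that eye matters because Section 11.1 counts any hospitalization or life-threatening event as serious, and systemic illness should not be scored as visual failure.

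The cost is edits to three protocol sections, one SAP line, a few retained visits that Table 2 already schedules, and possibly a slightly less favourable 20/40 rate. The change concerns data collection only and alters no treatment rule.
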